6.3.1 Disease Parameters

Measurable disease: Measurable lesions are defined as those that can be accurately measured in at least one dimension (longest diameter to be recorded) as:

- By chest x-ray: ≥ 20 mm;
- By CT scan:
 - Scan slice thickness 5 mm or under: as ≥ 10 mm
 - Scan slice thickness >5 mm: double the slice thickness
- With calipers on clinical exam: ≥ 10 mm.

All tumor measurements must be recorded in millimeters (or decimal fractions of centimeters).

Tumor lesions that are situated in a previously irradiated area may be considered measurable if there is demonstrated progression in the radiated lesion prior to starting on the trial.

Malignant lymph nodes. To be considered pathologically enlarged and measurable, a lymph node must be ≥ 15 mm in short axis when assessed by CT scan (CT scan slice thickness recommended to be no greater than 5 mm). At baseline and in follow-up, only the short axis will be measured and followed.

Non-measurable disease. All other lesions (or sites of disease), including small lesions (longest diameter <10 mm or pathological lymph nodes with ≥ 10 to <15 mm short axis), are considered non-measurable disease. Bone lesions, leptomeningeal disease, ascites, pleural/pericardial effusions, lymphangitis cutis/pulmonitis, inflammatory breast disease, and abdominal masses (not followed by CT or MRI), are considered as non-measurable.

Note: Cystic lesions that meet the criteria for radiographically defined simple cysts should not be considered as malignant lesions (neither measurable nor non-measurable) since they are, by definition, simple cysts.

‘Cystic lesions’ thought to represent cystic metastases can be considered as measurable lesions, if they meet the definition of measurability described above. However, if non-cystic lesions are present in the same participant, these are preferred for selection as target lesions.

Target lesions. All measurable lesions up to a maximum of 2 lesions per organ and 5 lesions in total, representative of all involved organs, should be identified as **target lesions** and recorded and measured at baseline. Target lesions should be selected on the basis of their size (lesions with the longest diameter), be representative of all involved organs, but in addition should be those that lend themselves to reproducible repeated measurements. It may be the case that, on occasion, the largest lesion does not lend itself to reproducible measurement in which circumstance the next largest lesion which can be measured reproducibly should be selected. A sum of the diameters (longest for non-nodal lesions, short axis for nodal lesions) for all target lesions will be calculated and reported as the baseline sum diameters. If lymph nodes are to be included in the sum, then only the short axis is added into the sum. The baseline sum diameters will be used as reference to further characterize any objective tumor regression in the measurable dimension of the disease.

Non-target lesions. All other lesions (or sites of disease) including any measurable lesions over and above the 5 target lesions should be identified as **non-target lesions** and should also be recorded at baseline. Measurements of these lesions are not required, but the presence, absence, or in rare cases unequivocal progression of each should be noted throughout follow-up.

6.3.2 Methods for Evaluation of Measurable Disease

All measurements should be taken and recorded in metric notation using a ruler or calipers. All baseline evaluations should be performed as closely as possible to the beginning of treatment and never more than 4 weeks before the beginning of the treatment.

The same method of assessment and the same technique should be used to characterize each identified and reported lesion at baseline and during follow-up. Imaging-based evaluation is preferred to evaluation by clinical examination unless the lesion(s) being followed cannot be imaged but are assessable by clinical exam.

Clinical lesions: Clinical lesions will only be considered measurable when they are superficial (e.g., skin nodules and palpable lymph nodes) and ≥ 10 mm diameter as assessed using calipers (e.g., skin nodules). In the case of skin lesions, documentation by color photography, including a ruler to estimate the size of the lesion, is recommended.

Chest x-ray: Lesions on chest x-ray are not acceptable as measurable lesions.

Conventional CT and MRI: This guideline has defined measurability of lesions on CT scan based on the assumption that CT slice thickness is 5 mm or less. If CT scans have slice thickness greater than 5 mm, the minimum size for a measurable lesion should be twice the slice thickness. MRI is also acceptable in certain situations (e.g. for body scans).

Use of MRI remains a complex issue. MRI has excellent contrast, spatial, and temporal resolution; however, there are many image acquisition variables involved in MRI, which greatly impact image quality, lesion conspicuity, and measurement. Furthermore, the availability of MRI is variable globally. As with CT, if an MRI is performed, the technical specifications of the scanning sequences used should be optimized for the evaluation of the type and site of disease. Furthermore, as with CT, the modality used at follow-up should be the same as was used at baseline and the lesions should be measured/assessed on the same pulse sequence. It is beyond the scope of the RECIST guidelines to prescribe specific MRI pulse sequence parameters for all scanners, body parts, and diseases. Ideally, the same type of scanner should be used and the image acquisition protocol should be followed as closely as possible to prior scans. Body scans should be performed with breath-hold scanning techniques, if possible.

PET-CT: At present, the low dose or attenuation correction CT portion of a combined PET-CT is not always of optimal diagnostic CT quality for use with RECIST measurements. However, if the site can document that the CT performed as part of a PET-CT is of identical diagnostic quality to a diagnostic CT (with IV and oral contrast), then the CT portion of the PET-CT can be used for RECIST measurements and can be used interchangeably with conventional CT in accurately measuring cancer lesions over time. Note, however, that the PET portion of the CT introduces additional data which may bias an investigator if it is not routinely or serially performed.

Ultrasound: Ultrasound is not useful in assessment of lesion size and should not be used as a method of measurement. Ultrasound examinations cannot be reproduced in their entirety for independent review at a later date and, because they are operator dependent, it cannot be guaranteed that the same technique and measurements will be taken from one assessment to the next. If new lesions are identified by ultrasound in the course of the study, confirmation by CT or MRI is advised. If there is concern about radiation exposure at CT, MRI may be used instead of CT in selected instances.

Endoscopy, Laparoscopy: The utilization of these techniques for objective tumor evaluation is not advised. However, such techniques may be useful to confirm complete pathological response when biopsies are obtained or to determine relapse in trials where recurrence following complete response (CR) or surgical resection is an endpoint.

Tumor markers: Tumor markers alone cannot be used to assess response. If markers are initially above the upper normal limit, they must normalize for a participant to be considered in complete clinical response. Specific guidelines for both CA-125 response (in recurrent ovarian cancer) and PSA response (in recurrent prostate cancer) have been published. [94-96] In addition, the

Gynecologic Cancer Intergroup has developed CA-125 progression criteria which are to be integrated with objective tumor assessment for use in first-line trials in ovarian cancer.[\[97\]](#)

Cytology, Histology: These techniques can be used to differentiate between partial responses (PR) and complete responses (CR) in rare cases (e.g., residual lesions in tumor types, such as germ cell tumors, where known residual benign tumors can remain).

The cytological confirmation of the neoplastic origin of any effusion that appears or worsens during treatment when the measurable tumor has met criteria for response or stable disease is mandatory to differentiate between response or stable disease (an effusion may be a side effect of the treatment) and progressive disease.

FDG-PET: While FDG-PET response assessments need additional study, it is sometimes reasonable to incorporate the use of FDG-PET scanning to complement CT scanning in assessment of progression (particularly possible 'new' disease). New lesions on the basis of FDG-PET imaging can be identified according to the following algorithm:

- a. Negative FDG-PET at baseline, with a positive FDG-PET at follow-up is a sign of PD based on a new lesion.
- b. No FDG-PET at baseline and a positive FDG-PET at follow-up: If the positive FDG-PET at follow-up corresponds to a new site of disease confirmed by CT, this is PD. If the positive FDG-PET at follow-up is not confirmed as a new site of disease on CT, additional follow-up CT scans are needed to determine if there is truly progression occurring at that site (if so, the date of PD will be the date of the initial abnormal FDG-PET scan). If the positive FDG-PET at follow-up corresponds to a pre-existing site of disease on CT that is not progressing on the basis of the anatomic images, this is not PD.
- c. FDG-PET may be used to upgrade a response to a CR in a manner similar to a biopsy in cases where a residual radiographic abnormality is thought to represent fibrosis or scarring. The use of FDG-PET in this circumstance should be prospectively described in the protocol and supported by disease-specific medical literature for the indication. However, it must be acknowledged that both approaches may lead to false positive CR due to limitations of FDG-PET and biopsy resolution/sensitivity.

Note: A 'positive' FDG-PET scan lesion means one which is FDG avid with an uptake greater than twice that of the surrounding tissue on the attenuation corrected image.

Evaluation of Target Lesions

Complete Response (CR): Disappearance of all target lesions. Any pathological lymph nodes (whether target or non-target) must have reduction in short axis to <10 mm.

Partial Response (PR): At least a 30% decrease in the sum of the diameters of target lesions, taking as reference the baseline sum of diameters.

Progressive Disease (PD): At least a 20% increase in the sum of the diameters of target lesions, taking as reference the smallest sum on study (this includes the baseline sum if that is the smallest on study). In addition to the relative increase of 20%, the sum must also demonstrate an absolute increase of at least 5 mm. (Note: the appearance of one or more new lesions is also considered progressions).

Stable Disease (SD): Neither sufficient shrinkage to qualify for PR nor sufficient increase to qualify for PD, taking as reference the smallest sum of diameters while on study.

Evaluation of Non-Target Lesions

Complete Response (CR): Disappearance of all non-target lesions and normalization of tumor marker level. All lymph nodes must be non-pathological in size (<10 mm short axis).

Note: If tumor markers are initially above the upper normal limit, they must normalize for a participant to be considered in complete clinical response.

Non-CR/Non-PD: Persistence of one or more non-target lesion(s) and/or maintenance of tumor marker level above the normal limits.

Progressive Disease (PD): Appearance of one or more new lesions and/or *unequivocal progression* of existing non-target lesions. *Unequivocal progression* should not normally trump target lesion status. It must be representative of overall disease status change, not a single lesion increase.

Although a clear progression of “non-target” lesions only is exceptional, the opinion of the treating physician should prevail in such circumstances, and the progression status should be confirmed at a later time by the review panel (or Principal Investigator).

Evaluation of Best Overall Response

The best overall response is the best response recorded from the start of the treatment until disease progression/recurrence (taking as reference for progressive disease the smallest measurements recorded since the treatment started). The participant's best response assignment will depend on the achievement of both measurement and confirmation criteria.

Table 12. Response Criteria for Participants with Measurable Disease (i.e., Target Disease)

Target Lesions	Non-Target Lesions	New Lesions	Overall Response	Best Overall Response when Confirmation is Required*
CR	CR	No	CR	≥ 4 to 8 wks. Confirmation**
CR	Non-CR/Non-PD	No	PR	
CR	Not evaluated	No	PR	
PR	Non-CR/Non-PD/not evaluated	No	PR	
SD	Non-CR/Non-PD/not evaluated	No	SD	Documented at least once ≥ 4 wks. from baseline**
PD	Any	Yes or No	PD	no prior SD, PR or CR
Any	PD***	Yes or No	PD	

Any	Any	Yes	PD
* See RECIST 1.1 manuscript for further details on what is evidence of a new lesion.			
** Only for non-randomized trials with response as primary endpoint.			
*** In exceptional circumstances, unequivocal progression in non-target lesions may be accepted as disease progression.			

Note: Participants with a global deterioration of health status requiring discontinuation of treatment without objective evidence of disease progression at that time should be reported as “symptomatic deterioration.” Every effort should be made to document the objective progression even after discontinuation of treatment.
			

For Participants with Non-Measurable Disease (i.e., Non-Target Disease)

Non-Target Lesions	New Lesions	Overall Response
CR	No	CR
Non-CR/non-PD	No	Non-CR/non-PD*
Not all evaluated	No	not evaluated
Unequivocal PD	Yes or No	PD
Any	Yes	PD

* ‘Non-CR/non-PD’ is preferred over ‘stable disease’ for non-target disease since SD is increasingly used as an endpoint for assessment of efficacy in some trials so to assign this category when no lesions can be measured is not advised

6.3.3 iRECIST

As an exploratory endpoint antitumor activity will also be evaluated according to iRECIST.[\[98\]](#) Using iRECIST criteria the following will be incorporated into the assessment:

- An increase in the sum of target lesions of more than 20%, unequivocal increase in the non-target lesions or new lesions result in iUPD (unconfirmed progression disease); iUPD can be assigned multiple ties as long as iCPD (confirmed progressive disease) is not confirmed at the next assessment.
- Progression is confirmed in the target lesion category if the next imaging assessment after iUPD (4-8 weeks later) confirms a further increase in sum of measures of target disease from iUPD, with an increase of at least 5mm. Progression is confirmed in the non-target lesion category if subsequent imaging, done every 4-8 weeks after iUPD shows a further unequivocal increase in non-target lesions. Progression is confirmed in the new lesions category if at next assessment additional new lesions appear or an increase in the size of previously seen new lesions is seen (≥ 5 mm for sum of new target lesion).

However, the criteria for iCPD (after iUPD) are not considered to have been met if complete response, partial response or stable disease criteria (compared with baseline and as defined by RECIST 1.1) are met at the next assessment after iUPD. The status is reset (unlike RECIST 1.1, in which any progression precludes later complete response, partial response, or stable disease). iCR, iPR, or iSD should then be assigned; and if no change is detected, then the timepoint response is iUPD.

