1. INTRODUCTION

1.1 STUDY OBJECTIVES

1.1.1 Primary Objectives:

- Arm 1 (Sequential Dose Escalation):
 - To evaluate the safety and tolerability of single agent SX-682.
 - To determine the MTD of SX-682 followed by M7824 and CV301 vaccines in participants with advanced or metastatic solid tumors. If the MTD is not reached the study will be focused to describe the safety and tolerability of SX-682 followed by M7824 and CV301 vaccines.
- Arm 2 (Combination Dose Escalation):
 - To determine the RP2D of SX-682 with M7824 and CV301 vaccines in participants with advanced or metastatic solid tumors. If the MTD is not reached the study will be focused to describe the safety and tolerability of the drug combination.
- Arm 3 (Expansion):
 - To evaluate preliminary efficacy based on objective response rate (ORR), in each disease cohort separately.

1.1.2 Secondary Objectives:

- Arms 1 and 2 (Dose Escalations):
 - To characterize the PK/PD profile of SX-682 as a single agent and in combination.
- All Arms:
 - To evaluate preliminary efficacy: disease control rate (DCR; CR+PR+SD) and progression-free survival (PFS) using RECIST1.1.

[figure not shown]
1.1.3 Exploratory Objectives (may be performed on selected participants if there are adequate samples.):

- All Arms:
 - To evaluate the effect on immune cell subsets and soluble factors in peripheral blood.
 - To evaluate the effect on cytokine levels (IL-8, IL-6 and others) in peripheral blood.
 - To evaluate the effect on T cell clonality in peripheral blood and tumor samples.
 - To evaluate the effect on antigen-specific T cells responses to CEA, MUC1 and the cascade antigen brachyury in peripheral blood.
 - To evaluate the effect on antigen-specific T cell responses to CEA, MUC1 and the cascade antigen brachyury in tumor biopsies.

- To evaluate the presence of lymphocytic and myeloid cell infiltrates and other tumor markers as well as to evaluate RNA expression for IL-8, TGF- β and other soluble factors in tumor biopsies.
- To evaluate clinical responses (ORR, and DCR) per iRECIST
- To evaluate M7824 PK profile in this drug combination
- To evaluate ADA in this drug combination
- To evaluate long term (2 years after completion of treatment) clinical outcomes
- To evaluate circulating tumor cells (CTCs)
- In Arms 1 and 2 (Dose-Escalation Cohort), the following are the parameters will be evaluated, separately per dose level:
 - To evaluate ORR per RECISTv1.1

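### Section 6.3.3 assigns iUPD without the 5 mm minimum or reference sum that 6.3.2 requires for PD, so for sums below 25 mm one scan can be both SD and iUPD

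*Combined protocol and SAP*

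**What the plan says.** Section 6.3.2 defines target-lesion progression with two conditions. The relative one is "At least a 20% increase in the sum of the diameters of target lesions, taking as reference the smallest sum on study". The absolute one is "In addition to the relative increase of 20%, the sum must also demonstrate an absolute increase of at least 5 mm". Stable disease is what remains: "Neither sufficient shrinkage to qualify for PR nor sufficient increase to qualify for PD".

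Section 6.3.3 sets the iRECIST rule for unconfirmed progression as follows: "An increase in the sum of target lesions of more than 20%, unequivocal increase in the non-target lesions or new lesions result in iUPD". For target lesions, the 5 mm figure appears only at the confirmation step, where the next scan "confirms a further increase in sum of measures of target disease from iUPD, with an increase of at least 5mm". The last paragraph of 6.3.3 resets the status if CR, PR or SD by RECIST 1.1, judged against baseline, is met at the next scan. It then adds that "if no change is detected, then the timepoint response is iUPD".

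The endpoint concerned is in section 1.1.3, for all arms: "To evaluate clinical responses (ORR, and DCR) per iRECIST". Section 10.4.10 lists iRECIST response among the exploratory analyses, with descriptive statistics.

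**The concern.** Both sections grade the same measurements, but they draw the line for first progression in different places. The 6.3.3 line is looser for small tumours, because the absolute minimum is absent. It is marginally stricter at the boundary, because growth must exceed 20% and not merely reach it. It also leaves open whether growth is counted from baseline or from the smallest sum.

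At stake is the coding of an exploratory endpoint. A participant with small-volume disease can be recorded as SD under RECIST 1.1 and as iUPD under 6.3.3 on the same scan. If no iSD, iPR or iCR is assigned later, that participant may count towards disease control under one criterion and not under the other. The cause would then be the wording of the threshold.

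**Working it through.** The documents give no expected rate or sample size for iRECIST disease control, so there is no stated figure to reproduce. The check compares the two written rules.

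**Inputs.** PD: increase of at least 20% and at least 5 mm over the smallest sum (6.3.2). iUPD: increase above 20% (6.3.3). Confirmation for target lesions: a further 5 mm from iUPD (6.3.3). Smallest measurable lesion by CT: 10 mm (6.3.1), so sums below 25 mm are admissible. Full cohort sizes: 21 for TNBC and 16 for HNSCC (10.2).

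**Where the rules part.** Let S be the reference sum, taken as the smallest on study for both rules. iUPD starts above 1.2 × S. PD starts at the larger of 1.2 × S and S + 5. These coincide when 0.2 × S = 5, that is S = 25 mm. Below that, the gap is 5 − 0.2 × S.

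| S (mm) | iUPD above | PD from | Gap (mm) |
|---|---|---|---|
| 10 | 12.0 | 15 | 3.0 |
| 15 | 18.0 | 20 | 2.0 |
| 20 | 24.0 | 25 | 1.0 |
| 24 | 28.8 | 29 | 0.2 |
| 25 | 30.0 | 30 | 0 |
| 50 | 60.0 | 60 | 0 |

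If sums are recorded in whole millimetres, the gap contains a value only for S from 10 to 19 mm. From 25 mm upward the only difference left is equality: 50 to 60 mm is +20% and +10 mm, so PD but not iUPD.

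**Effect on disease control, by sequence (baseline first).**

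- 20, 24.5, 30 mm. First restaging: +4.5 mm, +22.5%, so SD and iUPD. Next scan: +10 mm over the smallest sum, so PD; and +5.5 mm from iUPD, so iCPD. RECIST 1.1 best response is SD, since restaging at 6 weeks (Arms 1 and 2) or 8 weeks (Arm 3) in section 3.5 passes the 4-week minimum in Table 12. No iSD is ever assigned.
- 15, 19, 25 mm. The same pattern in whole millimetres: +4 mm (+26.7%), then +10 mm over baseline and +6 mm from iUPD.
- 15, 19, 17 mm. SD and iUPD, then SD against baseline (+2 mm). The reset gives iSD, and disease control agrees.
- 30, 20, 24.5 mm. PR is recorded at 20 mm (−33.3%), so the later iUPD does not change disease control.

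**Missing reference sum.** For 50, 30, 40 mm the last scan is +33.3% over the smallest sum but −20% from baseline. Section 6.3.3 does not say which applies. PR is already recorded (−40%), so this affects the date of iUPD and not disease control.

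**Size per participant.** 1/21 = 4.8 points; 1/16 = 6.3 points.

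**The no-change rule.** For 15, 19, 19 mm the last scan meets SD against baseline (+4 mm), which points to iSD, yet nothing has changed since iUPD, which points to iUPD. Aligning the threshold removes this example, because 19 mm would no longer be iUPD. It does not remove 50, 35.5, 45, 45 mm. There the third scan is +9.5 mm and +26.8% over the smallest sum, so iUPD under either threshold. The fourth is −10% from baseline and unchanged since iUPD.

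**The case against.** The best reply is that 6.3.3 says assessment follows iRECIST and cites the guideline, so the bullet may be an incomplete summary and the 5 mm minimum may apply through the source. That cannot be checked from the documents. It also does not remove the conflict in the protocol's own text, which states 5 mm at the confirmation steps and omits it at first progression.

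Other parts of the reply stand. A reader might infer that the iRECIST disease control rate will fall. The documents do not support that: the reset restores iSD in some sequences, an earlier SD or PR already counts, and the exactly-20% case runs the other way. A reader might also infer that a planned comparison of RECIST 1.1 with iRECIST would be distorted. No such comparison is planned; sections 1.1.3 and 10.4.10 ask only that iRECIST outcomes be evaluated. Nor do the documents give the share of participants with sums below 25 mm, or the chance of landing in a gap that is 1 mm wide at 20 mm, so no expected count can be derived.

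Finally, the no-change sentence can be read in order: assign iSD if SD is met, otherwise keep iUPD. That reading is reasonable but not stated, and the ambiguity is separate from the threshold.

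**Conclusion.** The conflict in the written rules is real, and its consequence is small. For reference sums below 25 mm, growth above 20% but under 5 mm is SD by 6.3.2 and iUPD by 6.3.3; growth of exactly 20% with at least 5 mm is PD but not iUPD.

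The exploratory iRECIST disease control rate can be lower than the RECIST 1.1 rate only where four conditions hold together: the baseline sum is under 25 mm, it is the smallest on study, the first restaging falls in the gap, and no iSD, iPR or iCR follows. This also assumes that participants with iUPD and no better iRECIST status count as not controlled, which the documents do not say. The number affected is unknown and may be zero.

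The primary ORR (6.3), the secondary DCR and PFS (1.1.2) and the confirmation of progression before removal from treatment (6.3) all use RECIST 1.1. The two-stage decisions (10.2, 10.4.7) use response counts. None of these changes, nor do sample size, alpha or power.

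**What to change.** In 6.3.3, replace the target-lesion threshold for iUPD with a statement that iUPD is assigned when the PD criteria of section 6.3.2 are first met: target sum at least 20% and at least 5 mm above the smallest sum on study including baseline, unequivocal non-target progression, or new lesions. This closes the gap below 25 mm, removes the exactly-20% mismatch and supplies the reference sum. The confirmation criteria can stay as they are.

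Separately, state in the last paragraph of 6.3.3 which assignment applies when SD against baseline is met but the sum is unchanged since iUPD. The threshold edit does not settle that case. While the section is open, it would help to say how participants with only iUPD count in iRECIST disease control.

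The cost is a few lines of text. No new data are needed, and no sample size or treatment rule changes.
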